The study conduct was substantially impacted by the COVID-19 pandemic. In particular, the pandemic caused delayed and missed visits to several subjects in the randomized dose expansion phase of the study. In addition, there were delays beyond the planned 6 months for treatment in the deferred treatment arm of the study. To allow greater flexibility in the management of protocol

deviations and timing of treatments in the deferred treatment arm of the study as a result of the COVID-19 pandemic, the protocol was amended in accordance with Health Authority guidance.

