2. GENERAL ANALYSIS DEFINITIONS

2.1. Visit Windows

The following rules are applied to assign actual visits to analysis visit windows. If a subject has two or more actual visits in 1 visit window, the visit closest to the target day will be used as the protocol visit for that visit window. The additional visit(s) will not be used in the summaries or analyses, but they can be used for determination of clinically important outcomes. If two actual visits are equidistant from the target day within a visit window, the later visit is used. All assignments will be made in chronological order. Once a visit date is assigned to a visit window, it will no longer be used for a later time point. If a visit falls outside of the visit window, then this visit will be assigned to the closest window according to the distance to the target day and visit description, if there is no visit assigned to the visit window.

Table 1: Visit Windows

| Dose Escalation Phase, Pediatric Dose Confirmation Phase, and Immediate Treatment Arms of Expansion Phase | | |
|--|----------------------|-------------------|
| Visit Window Label | Time Interval | Target Day |
| Baseline | -6 Months - Day -1 | < Day 1 |
| Day 1 (ATIMP admin.) | Day 1 | Day 1 |
| Day 2 | Day 2 | Day 2 |
| Day 4 | Day 3 – Day 5 | Day 4 |
| Week 1 | Day 6 – Day 10 | Day 8 |
| Week 2 | Day 11 – Day 21 | Day 15 |
| Week 4 | Day 22 – Day 36 | Day 29 |
| Week 6 | Day 37 – Day 56 | Day 43 |

| Week 9 | Day 57 – Day 72 | Day 64 | |
|---|----------------------|---------------------|------------|
| Week 13 | Day 73 – Day 160 | Day 92 | |
| Week 26 | Day 161 – Day 259 | Day 183 | |
| Week 39 | Day 260 – Day 350 | Day 274 | |
| Week 52 | Day 351 – Day 393 | Day 365 | |
| Deferred Treatment Arms of Expansion Phase | | | |
| Period | Visit Window Label | Time Interval | Target Day |
| Deferred Period (prior to treatment) | Baseline | -6 Months - Day 1 | ≤ Day 1 |
| | Week 13 | Day 73 – Day 168 | Day 92 |
| | Week 26 | Day 169 – Day 365 † | Day 183 |
| Post treatment period | Day 1 (ATIMP admin.) | Day 1 | Day 1¶ |
| | Day 2 | Day 2 | Day 2¶ |
| | Day 4 | Day 3 – Day 5 | Day 4¶ |
| | Week 1 | Day 6 – Day 10 | Day 8¶ |
| | Week 2 | Day 11 – Day 21 | Day 15¶ |
| | Week 4 | Day 22 – Day 36 | Day 29¶ |
| | Week 6 | Day 37 – Day 56 | Day 43¶ |
| | Week 9 | Day 57 – Day 72 | Day 64¶ |
| | Week 13 | Day 73 – Day 160 | Day 92¶ |
| | Week 26 | Day 161 – Day 365 † | Day 183¶ |

¶: after ATIMP administration day for deferred subjects

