 † : Any scheduled visits after week 26 in deferred treatment arm will be summarized as week 26 visits given COVID-19 delays

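### The control arm's Week 26 window runs to Day 365 and the immediate arms' only to Day 259, so the randomised Week 26 comparison can use different elapsed times by arm

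*SAP*

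**What the plan says.** The visit-window table in SAP 2.1 sets Week 26 at "Day 161 – Day 259" for the immediate arms and "Day 169 – Day 365" for the deferred arm before treatment, both with target Day 183. The footnote explains the longer control window: "Any scheduled visits after week 26 in deferred treatment arm will be summarized as week 26 visits given COVID-19 delays". The immediate arms have later windows that take over after Day 259: Week 39 (Day 260–350) and Week 52 (Day 351–393). The deferred period has none.

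SAP 1.3.2 and 5.3.1 place the primary comparison at Week 26 in the randomised expansion phase and describe the control period as 26 weeks. SAP 1.2 reports delayed and missed visits in the expansion phase generally, and adds that "there were delays beyond the planned 6 months for treatment in the deferred treatment arm of the study".

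Three other SAP rules matter here. Where a window holds several visits, the one closest to target is used (2.1). A visit outside every window goes to the closest window that is still empty (2.1). A subject without both Week 13 and Week 26 leaves the responder denominator (5.3.1).

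**The concern.** The Week 26 label should mean the same thing in both randomised arms. Here the control arm may supply a value up to a year after its Day 1, while the immediate arms may not. The pandemic affected visits across the expansion phase, but only one arm's window was lengthened.

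Two things follow. First, a late control value contains more natural decline than an on-time one, which would widen the apparent treatment difference in V30, microperimetry, mobility and EZ area. Second, late visitors are handled differently. A control seen only on Day 300 stays in the Week 26 analysis. A treated participant seen only on Day 300 is labelled Week 39, has no Week 26 value, and drops out of the responder denominator.

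Nothing planned would reveal the effect on the randomised comparison. The V30 model, which the other secondary endpoints share, uses nominal visit month (SAP 5.4.2). The sensitivity analyses pool study phases (1.3.2, 2.2), add natural history data (2.2) or drop unreliable perimetry (5.2.1); none uses a common window or actual time. COVID-19 delays are only tabulated and listed (4.4).

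**Working it through.** The documents give no figure to reproduce for this point, so the check is day arithmetic on the SAP 2.1 table, followed by illustrations on stated assumptions.

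**1. Windows (SAP 2.1)**
- Width: immediate 259 − 161 + 1 = 99 days; control 365 − 169 + 1 = 197 days.
- Latest visit after target: 259 − 183 = 76 days; 365 − 183 = 182 days.
- Gap between upper limits: 365 − 259 = 106 days (15.1 weeks). These 106 days are 106/197 = 54% of the control window, and in the immediate arms they belong to Week 39 or Week 52.
- Largest permitted gap: control later, 365 − 161 = 204 days; immediate later, 259 − 169 = 90 days.
- Week 13 upper limits: 168 − 160 = 8 days apart.

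**2. Elapsed time from Day 1.** Day 183 is 182 days after Day 1. A control at the upper limit has 364/182 = 2.0 times that interval; an immediate-arm visit at its limit has 258/182 = 1.42 times.

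**3. Elapsed time from baseline.** The endpoints are changes from baseline, so this is the interval that matters. Day 1 is surgery in the immediate arms but the end of the last baseline visit in the deferred arm (SAP 2.5). The immediate-arm baseline may lie up to 6 months before surgery (SAP 2.1), and Protocol Appendix 1 extends baseline validity to 6 months where surgery was postponed. Taking 6 months as 183 days:
- immediate arm, test on target: 183 + 182 = 365 days;
- immediate arm, test at the upper limit: 183 + 258 = 441 days, or 441/182 = 2.4 times the nominal interval;
- control at Day 365 with baseline on Day 1: 364 days, somewhat longer when earlier baseline visits are averaged in (SAP 2.6).

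At these extremes the baseline gap can match or exceed the window gap.

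**4. Continuous endpoint, window effect alone.** Assumptions: no treatment effect, linear decline d (SD per year), a fraction f of controls seen at Day 365, everyone else at Day 183, equal baseline intervals, 32 vs 16 subjects. Shift = d × f × 182/365.25. Standard error = √(1/32 + 1/16) = 0.306 SD. Two-sided error = Φ(shift/0.306 − 1.96) + Φ(−shift/0.306 − 1.96).

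| d (SD/year) | f | shift (SD) | error at nominal 0.05 |
|---|---|---|---|
| 0.1 | 0.5 | 0.025 | 0.051 |
| 0.25 | 0.25 | 0.031 | 0.051 |
| 0.5 | 0.5 | 0.125 | 0.069 |
| 0.5 | 1.0 | 0.249 | 0.129 |

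**5. Responder endpoint.** This is exact enumeration of the unstratified two-sided Fisher test at 32 vs 16. The SAP specifies a stratified version, so it is a guide only. The table gives the chance of a significant result favouring treatment when treatment does nothing, with and without an assumed halving of the control rate by lateness.

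| true response rate | no lateness effect | control rate halved |
|---|---|---|
| 10% | 0.002 | 0.005 |
| 20% | 0.013 | 0.070 |
| 30% | 0.014 | 0.144 |

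The documents give neither an untreated response rate nor any basis for the halving.

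**The case against.** The case for the sponsor has real force on direction, size and remedy.

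- **Direction.** A reader might infer that the rule biases the trial towards treatment. The documents do not support that as a net statement. Step 3 shows that early immediate-arm baselines can offset the window difference or outweigh it. Nothing makes the two intervals cancel, however, so this leaves the net direction unknown; it does not remove the problem.
- **The primary test.** A reader might apply the error rates in step 4 to the primary analysis. They belong to a continuous endpoint tested alone. The primary is a responder test that also needs improvement at Week 13, where the windows nearly match. Under SAP 5.5, V30 is tested only if the primary succeeds, and mobility only after V30, so these rates also overstate the chance of a false formal claim when nothing works.
- **Occurrence.** A reader might infer that many control tests were late. SAP 1.2 reports late treatment in the deferred arm, which is not the same as a late Month 6 test. Protocol Table 4 schedules that test before administration, within about 14 days of Month 6, and the closest-to-target rule prefers an on-time visit if there was one. The number of tests after Day 259 is not stated.
- **Remedy.** Making exclusion of late controls the primary rule is debatable. There are at most 16 controls, and each exclusion shrinks the randomised denominator.

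All four limits stand. None of them explains why one arm's window should be longer, or supplies the missing check.

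**Conclusion.** The SAP allows the randomised Week 26 comparison to use different elapsed times by arm, with upper limits 106 days apart, and it retains late visitors in one arm while relabelling them in the other. This follows directly from the visit-window table.

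The window difference alone would be expected to favour treatment, mainly on V30, microperimetry, mobility and EZ area. Under the assumptions in step 4, the error rate for a continuous endpoint ranges from barely above 5% to about 13%. The effect on the responder primary should be smaller because of the Week 13 requirement. It exceeds 5% in step 5 only if untreated response is 20–30% and lateness halves it.

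The net direction and size cannot be settled from the documents, because late control tests are not counted and baseline intervals also differ by arm. What is established is an uncontrolled timing difference without a planned check, not a demonstrated bias in the result.

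**What to change.** Add to the SAP:

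1. An analysis of the primary and secondary endpoints with identical windows in both arms: Week 13 at Day 73–160 and Week 26 at Day 161–259. The out-of-window reassignment rule in SAP 2.1 must be switched off for control visits after Day 259; otherwise it could return them to an empty Week 26 slot. The largest permitted gap between arms then becomes 259 − 161 = 98 days in either direction.
2. For the continuous endpoints, a model using actual time from baseline to assessment in place of nominal visit, stating how that time is measured when baseline is an average of several visits. This also addresses the baseline gap, which common windows do not.
3. A table by arm of the actual Week 26 day and the baseline-to-visit interval.
4. A statement that these results are reported beside the footnote-rule result, and that the Week 26 conclusion is limited if they disagree.

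The cost is SAP wording and some extra programming, with no new data. The common-window result loses precision if many controls were late. If 8 of 16 were excluded, the standard error would rise from √(1/32 + 1/16) = 0.306 to √(1/32 + 1/8) = 0.395 SD, about 29%. If few were late, the results should barely move and the concern is largely closed.

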2.2. Pooling Algorithm

In the primary efficacy analysis, randomized immediate treatment arm subjects (pooled low and intermediate doses) in the dose expansion phase will be compared with deferred treatment arm subjects in the dose expansion phase. As a supportive analysis, immediate treatment arm subjects at low, intermediate and high doses in the dose escalation phase and dose confirmation phases will be also compared with deferred treatment subjects prior to treatment in the dose expansion phase, respectively.

A sensitivity analysis will include subjects assigned to low and intermediate doses pooled across both dose escalation phase and expansion phases and compared with deferred subjects prior to treatment from the dose expansion phase of the study.

The MGT011 study is an ongoing long-term natural history non-interventional study of RPGR-XLRP subjects. Sixteen MGT009 subjects participated in the MGT011 study prior to enrolling into MGT009. The study procedures and timing of assessments in both MGT009 and MGT011 are similar thereby facilitating a longitudinal analysis. To do so, data from the deferred subjects prior to treatment from MGT009 (i.e., during their enrollment in the natural history study) will be included to create a more robust longitudinal data set that will help enhance the precision of the corresponding model estimates for this group and expand the deferred period data. This sensitivity analysis will be conducted using this pooled dataset to assess the progression of the disease prior to and post treatment.

2.3. Analysis Sets

2.3.1. All Enrolled Analysis Set

The analysis set of all enrolled subjects includes all subjects who were assigned to a treatment group and therefore excludes screen failures.

2.3.2. Efficacy Analysis Set(s)

For efficacy analyses, the Full Analysis Set (FAS) includes all subjects treated with ATIMP who completed both a baseline and at least one visit after ATIMP administration from the dose escalation and dose confirmation phases, and all immediate treatment subjects who were administered ATIMP and have both a baseline and at least one visit after ATIMP administration and all deferred subjects who completed at least one baseline visit and one post baseline visit prior to ATIMP administration from the expansion phase. Efficacy analyses will be performed according to the randomized/assigned treatment assignment.

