5.3.1.6.4 Enrolment (Randomisation)

Participants who fulfil the study entry criteria based on the results of all screening assessments will be enrolled (randomised) in the trial. ATIMP will be administered within 3 months of enrolment for participants randomised to immediate treatment. If the ATIMP is not delivered within 3 months of enrolment, all screening tests with the exception of genetic testing, visual mobility and electrophysiological assessment will be repeated and eligibility for enrolment re-assessed³. For participants randomised to the control (deferred treatment) arm, study assessments will be performed per the Table 4: Trial Assessments (Deferred treatment arm).

Participants who withdraw or are withdrawn from the study for any reason prior to ATIMP administration may be substituted in the study.

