5.4.9 Protocol Treatment Discontinuation

5.4.9.1 Participant withdrawal

In consenting to the trial, participants are consenting to ATIMP administration, trial follow-up and data collection.

As participation in the trial is entirely voluntary, the participant may choose to discontinue trial participation at any time without penalty or loss of benefits to which they would otherwise be entitled.

Although not obliged to give a reason for discontinuing their participation, a reasonable effort should be made to establish this, whilst remaining fully respectful of the participant's rights.

Should a participant withdraw from the study, a withdrawal CRF documenting the reason for withdrawal will be completed, in addition to the procedures and CRF for the final visit (12 month) assessments, with the participant's consent. However, participants will be encouraged to participate in any of the planned schedule for the trial whilst arranging a visit for routine (annual) clinical follow-up.

Participants who withdraw prior to vector administration will be regarded as off-protocol and their primary ophthalmologist will resume normal standard of care. Any participant who withdraws prior to administration of ATIMP may be replaced in the study. Participants who withdraw from the study after vector administration will be encouraged to have follow-up safety and efficacy investigations with their consent, so that the consequences of vector administration can be documented, and the data analysed. The CMT may choose to replace a participant who withdraws after vector administration.

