5.6.1 Early Stopping of Follow-up

If a participant chooses to discontinue their trial treatment, they should continue to be followed up as closely as possible to the follow-up schedule defined in the protocol, providing they are willing. If, however, the participant exercises the view that they no longer wish to be followed up either, this view must be respected. Data already collected will be kept and included in analyses according to the intention-to-treat principle for all participants who stop follow up early.

Participants who stop trial follow-up early may be replaced.

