5. EFFICACY

Unless otherwise specified, efficacy analyses will be based on the efficacy analysis set and statistical tests will be interpreted at a two-sided significance level of 0.05, with confidence intervals presented at a 2-sided level of 95%.

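### The efficacy set makes dosing a condition for the immediate arms only, so exclusions after randomisation are asymmetric in the primary comparison

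*SAP*

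**What the plan says.** SAP 2.3.2 defines the Full Analysis Set (FAS) separately for the two randomised groups of the expansion phase. From the immediate arms it takes "all immediate treatment subjects who were administered ATIMP and have both a baseline and at least one visit after ATIMP administration". From the deferred arm it takes "all deferred subjects who completed at least one baseline visit and one post baseline visit prior to ATIMP administration from the expansion phase". It then adds: "Efficacy analyses will be performed according to the randomized/assigned treatment assignment". SAP 5 states that, unless otherwise specified, "efficacy analyses will be based on the efficacy analysis set", so this definition governs the primary test and the sequence of secondary tests in SAP 5.5.

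The protocol leaves an interval in which the two rules can act differently. Baseline is measured after randomisation (Protocol 4.3.2.2.5). Immediate dosing may follow enrolment by up to 3 months, and if it is later most screening tests are repeated and eligibility is judged again (Protocol 5.3.1.6.4). The same section says: "Participants who withdraw or are withdrawn from the study for any reason prior to ATIMP administration may be substituted in the study".

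For the primary endpoint, SAP 5.3.1 also removes from the denominator anyone in either arm who lacks the Week 13 or the Week 26 visit. The primary estimand (SAP 5.3.2) names a treatment policy strategy but lists no intercurrent event, so being randomised and not dosed is not addressed.

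**The concern.** Analysing by randomised arm protects the comparison only if entry to the analysis set does not depend on what happens after randomisation, or at least depends on it in the same way in each arm. Here it does not. Declining surgery, or failing a repeat eligibility check before it, removes an immediate participant. A deferred participant with the same inclination or condition may meet that obstacle only after the control period, when the qualifying visits are already complete.

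SAP 1.4 says that visual function assessors and reading centres were masked but that site and sponsor staff were not. Decisions to withdraw or substitute someone could therefore be taken with the arm known. If those who drop out before surgery differ in prognosis or test reliability from those who stay, the pooled immediate group and the control group no longer differ by chance alone. The primary test opens the whole alpha sequence in SAP 5.5, so any bias there carries into every later claim. The planned sensitivity analyses (SAP 2.2 and 5.2.1) pool phases, add natural-history data or drop unreliable fields; none uses all randomised participants.

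**Working it through.** **Step 1. The two rules side by side.**

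| Situation | Immediate arm | Deferred arm |
|---|---|---|
| No baseline visit | out of FAS | out of FAS |
| Baseline, then leaves before any later visit | out of FAS | out of FAS |
| Baseline and a later visit, never dosed | out of FAS | in FAS |
| In FAS but Week 13 or Week 26 missing | out of primary denominator | out of primary denominator |
| Week 13 and Week 26 done, then declines surgery | cannot arise (Day 1 is the dosing day) | in FAS and in primary denominator |

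Rows 1, 2 and 4 treat the arms alike. Rows 3 and 5 do not. Row 3 matters most for the secondary endpoints, where one post-baseline visit is enough to enter the FAS; row 5 matters for the primary endpoint.

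**Step 2. Is there a figure to reproduce?** No. Protocol 5.7 gives no formal sample size calculation. The allocation counts agree: 16 + 16 + 16 = 48, so the pooled comparison is at most 16 + 16 = 32 immediate against 16 deferred.

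**Step 3. How much could it matter?** The documents do not report how many immediate participants were undosed. Assume k of 32, with r immediate and c deferred responders, no responder among the k, and everyone else complete at Weeks 13 and 26. Compare r/(32 − k) against c/16 (k dropped) with r/32 against c/16 (k kept as non-responders). The test is the two-sided Fisher exact test, unstratified; the SAP specifies a version stratified by age, which cannot be run without counts per stratum.

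Worked case, r = 7, c = 0. The probability of d deferred responders among 7 is C(16,d) × C(n,7−d) / C(n+16,7), where n is the immediate denominator. The two-sided p adds every table no more probable than the one observed.

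- n = 32: d = 0 gives 3,365,856 / 73,629,072 = 0.0457. Tables d = 5, 6, 7 (0.0294, 0.0035, 0.0002) are less probable and are added: p = 0.0788.
- n = 29: d = 0 gives 1,560,780 / 45,379,620 = 0.0344. Table d = 5 is now 0.0391, more probable than the observed table, so only d = 6 and 7 (0.0051, 0.0003) are added: p = 0.0398.

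Much of the fall in p is therefore the discreteness of the test. The estimated rate moves only from 7/32 = 21.9% to 7/29 = 24.1%.

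Range of assumptions (p-values; the k = 0 column is also the result for any k when the undosed are kept as non-responders):

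| r vs c | k = 0 | k = 1 | k = 2 | k = 3 | k = 4 |
|---|---|---|---|---|---|
| 6 vs 0 | 0.1595 | 0.0819 | 0.0782 | 0.0749 | 0.0718 |
| 7 vs 0 | 0.0788 | 0.0782 | 0.0782 | 0.0398 | 0.0370 |
| 8 vs 0 | 0.0394 | 0.0381 | 0.0371 | 0.0366 | 0.0365 |
| 10 vs 1 | 0.0727 | 0.0699 | 0.0679 | 0.0669 | 0.0363 |
| 12 vs 1 | 0.0363 | 0.0359 | 0.0182 | 0.0165 | 0.0151 |
| 13 vs 2 | 0.0567 | 0.0522 | 0.0487 | 0.0463 | 0.0451 |

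Three of these six rows cross 0.05, at k = 3, 4 and 2; the other three do not cross at any k shown.

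**Step 4. Would redefining the FAS be enough?** No. SAP 2.5 sets Study Day 1 for immediate participants at dosing, so an undosed one has no Week 13 or Week 26 window, and SAP 5.3.1 would then drop that person from the denominator anyway.

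**The case against.** A reader might infer that exclusions after randomisation fall on one arm only. The documents do not say that. A deferred participant without a baseline or a later pre-dosing visit is also excluded, and the Week 13 and Week 26 rule applies to both arms. What differs is the dosing condition.

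A reader might also infer that replacement is confined to the immediate arms. The substitution rule names no arm, and deferred participants spend at least 6 months undosed and so are exposed to it for longer. The further rule, "The CMT may choose to replace a participant who withdraws after vector administration", does not bear on the point: someone dosed, with a baseline and one later visit, stays in the FAS.

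Protocol 5.6.1 is weaker support than it looks. "Data already collected will be kept and included in analyses according to the intention-to-treat principle" concerns people who stop follow-up early; it does not promise an efficacy set of all randomised participants.

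Nor do the documents show that the pandemic left immediate participants undosed. The re-assessment rule carries a footnote to Protocol Appendix 1, which extends the validity of baseline to 6 months when surgery was postponed and requires only blood tests to be repeated. SAP 1.2 reports treatment delays in the deferred arm.

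Finally, the SAP cites protocol v12.0, while the amendment log of the protocol reviewed ends at v11.0, so the substitution and re-assessment rules may differ in the governing version. Part of the reporting is already planned: SAP 4.2 tabulates, by treatment group on the All Enrolled set, who was dosed and who discontinued.

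All of this stands, and it narrows the point. It does not remove it: the dosing condition in SAP 2.3.2 is on the page, applies to one side of the randomised comparison, and is not offset by any other rule or planned analysis.

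**Conclusion.** The point holds in this form: both arms have post-randomisation exclusions, but dosing is a condition of entry for the immediate arms only, so the exclusions are asymmetric and can bias the primary comparison in an open-label trial.

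Its size cannot be stated. It depends on how many immediate participants were randomised and not dosed, which the documents do not give. If nobody was, there is no effect. The direction is unknown too: the p-values above fall because the undosed are assumed to be non-responders, and participants lost selectively could differ in either direction. Within those assumptions, 3 undosed of 32 change the conclusion at 7 vs 0 responders (0.040 against 0.079) but not at 6 vs 0 (0.075 against 0.160) or 8 vs 0 (0.037 against 0.039). A claim that randomisation is undone, or that the primary result would reverse, goes beyond this evidence. With at most 48 participants and a test this discrete, though, a handful of exclusions can decide significance, which is reason enough to correct a definition that is easy to correct.

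**What to change.** 1. Define the expansion-phase efficacy set as all randomised participants in their randomised arm. The All Enrolled set of SAP 2.3.1, restricted to that phase, already serves.
2. Count replacements as additional randomised participants, never in place of the person replaced.
3. Give undosed immediate participants a Day 1, for example the end of the last baseline visit, as SAP 2.5 does for the deferred arm.
4. State a responder rule for anyone without Week 13 or Week 26 data, for example non-responder, applied equally in both arms. Without items 3 and 4, item 1 has no effect on the primary endpoint.
5. Keep the dosed-and-seen set as a sensitivity analysis.
6. Add replacement counts by arm to the disposition table in SAP 4.2.

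The cost is SAP text and a little more analysis; visits already missed cannot be recovered. The treated estimate is diluted if some were undosed. With assumed true rates of 40% and 5%, one undosed participant kept as a non-responder lowers the immediate rate to 40% × 31/32 = 38.8% and approximate power from 0.78 to 0.75. Four lower them to 40% × 28/32 = 35.0% and 0.66. The dilution is slight if few were undosed, and the sensitivity analysis shows the undiluted figure beside it.
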